**Male contraception:**

Male subjects must always use a condom.

**Vasectomy:**

Use of contraceptive methods applies also to vasectomized men.

**Pregnant female partners of male study participants:**

Male study participants must use condoms during intercourse if their female partners are pregnant.

## **APPENDIX F. LOST TO FOLLOW-UP**

A patient will be considered lost to follow-up if he/she repeatedly fails to return for scheduled visits and if the site is unable to establish contact with the patient after 3 documented attempts via 2 different methods (phone, text, e-mail, certified letter, etc).

The following actions must be taken if a patient fails to return to the investigational center for a required study visit:

- The investigational center must attempt to contact the patient and reschedule the missed visit as soon as possible and counsel the patient on the importance of maintaining the assigned visit schedule and ascertain whether or not the patient wishes to and/or should continue in the study.
- In cases in which the patient is deemed lost to follow-up, the investigator or designee must make every effort to regain contact with the patient (where possible, 3 telephone calls and, if necessary, a certified letter to the patient's last known mailing address or local equivalent methods). These contact attempts should be documented in the patient's medical record.
- Should the patient continue to be unreachable, he/she will be considered to have withdrawn from the study with a primary reason of 'lost to follow-up'.

## **APPENDIX G. HANDLING, LABELING, STORAGE, AND ACCOUNTABILITY FOR INVESTIGATIONAL MEDICINAL PRODUCT(S)**

### **Preparation of Investigational Medicinal Products**

Fremanezumab or placebo will be provided in prefilled syringes contained in uniquely numbered kits and stored accordingly (see above). At the time of each study visit, the IRT will be queried, and investigational site personnel will retrieve the appropriately numbered kit(s). Kit numbers will be entered into the CRF.

Preparation instructions for iv infusions: Investigational medicinal product (IMP) syringes should be allowed to equilibrate at room temperature for 45 to 60 minutes before administration into the iv bag. The contents of 4 prefilled syringes, each containing fremanezumab (225 mg/1.5 mL) or 1.5 mL of placebo, will be added to 500 mL of normal saline solution. The iv infusion will be administered over approximately 1 hour.

Preparation instructions for sc injections: IMP should be allowed to equilibrate at room temperature for 45 to 60 minutes before sc administration. A 1.5 mL volume from each syringe in each visit kit(s) must be injected sc for dosing to be considered complete. Refer to [Appendix U](#) for additional details regarding recommended sc injection sites.

### **Storage and Security**

The investigator or designee must confirm appropriate temperature conditions have been maintained for all IMPs received and any discrepancies are reported and resolved before use of the IMPs.

The test IMP (fremanezumab) and placebo IMP must be stored refrigerated at 2°C to 8°C (36°F to 46°F), protected from light; the investigational site should have a process for monitoring the drug storage temperature.

Diversions are considered to have occurred when the legal supply chain of prescription analgesic medicinal products is broken, and medicinal products are transferred from a licit to an illicit channel of distribution or use.

### **Labeling**

Supplies of IMPs will be labeled in accordance with the current International Council for Harmonisation (ICH) guidelines on Good Clinical Practice (GCP) and Good Manufacturing Practice and will include any locally required statements. If necessary, labels will be translated into the local language.

### **Accountability**

Each IMP shipment will include a packing slip listing the contents of the shipment, return instructions, and any applicable forms.

The investigator is responsible for ensuring that deliveries of IMPs and other study materials from the sponsor are correctly received, recorded, handled, and stored safely and properly in

accordance with the CFR or national and local regulations, and used in accordance with this protocol.

Only patients enrolled in the study may receive IMPs and only authorized staff at the investigational center may supply or administer IMPs. All IMPs must be stored in a secure, environmentally controlled, and monitored (manual or automated) area in accordance with the labeled storage conditions or appropriate instructions with access limited to the investigator and authorized staff at the investigational center.

The investigator, institution, or the head of the medical institution (where applicable) is responsible for IMP accountability, reconciliation, and record maintenance (ie, receipt, reconciliation, and final disposition records).

A record of IMP accountability (ie, IMP and other study materials received, used, retained, returned, or destroyed) must be prepared and signed by the principal investigator or designee, with an account given for any discrepancies. Empty and partially used prefilled syringes should be destroyed, and the investigational site should provide a certificate of destruction. If the investigational site does not have the capability to destroy the used and partially used prefilled syringes, the prefilled syringes should be sent back to the sponsor. Unused prefilled syringes of IMP will be returned to the sponsor or designee.

## **APPENDIX H. PREVENTIVE CLUSTER HEADACHE MEDICATIONS AND DISALLOWED MEDICATIONS**

### **1. Medications Commonly Prescribed for Cluster Headache**

The following medications will be considered as being used for the prevention of cluster headaches, regardless of the initial indication.

- verapamil
- lithium
- methysergide
- valproate
- topiramate

Patients are allowed to take up to 2 of these medications provided that they are on a stable dose and regimen for at least 2 weeks prior to screening and throughout the study.

Botox will not be a stable concomitant preventive medication for cluster headaches. If the patients were treated with Botox for the prevention of migraine, they should have had at least 2 cycles of Botox within 10 days of a new cluster cycle prior to screening.

### **2. Concomitant Medications Allowed and Disallowed**

#### Steroids:

Screening/run-in period and throughout the study: Systemic steroids are not allowed to be used in the treatment of cluster cycles during the screening/run-in period and for the duration of the study.

The only allowed steroids are intra-articular injection or ocular, ear drops, intranasal, inhaled, and creams for topical use.

Screening/run-in period: Disallowed if patient used systemic steroids to treat the current CH cycle or for any other indication to treat the current CH cycle within  $\leq 7$  days of screening.

#### Butalbital:

Screening/run-in period: Disallowed if used more than 10 days during the screening/run-in period. Patients can use butalbital as needed (PRN) after randomization into the study.

#### Opioids:

Screening/run-in period: Disallowed if used more than 15 days during the screening/run-in period. Patients can use opioids PRN after randomization into the study.

## **APPENDIX I. ICHD 3-BETA DIAGNOSTIC CRITERIA**

Refer to the ICHD 3-Beta Diagnostic Criteria ([Headache Classification Committee of the IHS 2013](#)) for additional details.

### **3.1 Cluster headache**

*Diagnostic criteria:*

- A) at least 5 attacks fulfilling criteria B-D
- B) severe or very severe unilateral orbital, supraorbital and/or temporal pain lasting 15 to 180 minutes (when untreated)
- C) either or both of the following:
  - 1) at least 1 of the following symptoms signs, ipsilateral to the headache:
    - a) conjunctival injection and/or lacrimation
    - b) nasal congestion and/or rhinorrhea
    - c) eyelid edema
    - d) forehead and facial sweating
    - e) forehead and facial flushing
    - f) sensation of fullness in the ear
    - g) miosis and/or ptosis
  - 2) a sense of restlessness or agitation
- D) attacks have a frequency of between 1 every other day and 8 per day for more than half of the time when the disorder is active
- E) not better accounted for by another ICHD 3-beta diagnosis

#### **3.1.1 Episodic cluster headache**

*Diagnostic criteria:*

- A) attacks fulfilling criteria for 3.1 Cluster headache and occurring in bouts (cluster period)
- B) at least 2 cluster periods lasting from 7 days to 1 year (when untreated) and separated by pain-free remission periods of  $\geq 1$  month

#### **3.1.2 Chronic cluster headache**

*Diagnostic criteria:*

- A) Attacks fulfilling criteria for 3.1 Cluster headache and criterion B
- B) Occurring without a remission period or with remissions lasting  $< 1$  month, for  $\geq 1$  year

---

 During part (but less than half) of the time course of 3.1 Cluster headache, attacks may be less severe and/or of shorter or longer duration.

## **APPENDIX J. GUIDANCE ON SAFETY MONITORING**

### **Guidance on Monitoring Patients with Elevated Liver Function Tests**

Liver enzymes (ALT, AST, GGT, and ALP) as well as total, direct, and indirect bilirubin will be measured at each study visit.

In any case of elevated ALT or AST to a level exceeding  $\geq 2 \times$  the ULN (including patients whose baseline ALT or AST levels are  $\geq 2 \times$  and  $\leq 3 \times$  the ULN, who may be enrolled in the study), a thorough medical history and physical examination with a focus on liver disease should be undertaken. In addition, the patient should be instructed to refrain from alcoholic beverages.

In case of symptoms compatible with drug-induced liver injury during the study, patients will be instructed to return to the study center for an unscheduled visit or to go to the emergency room to measure liver enzymes as soon as possible. Solitary elevations of total, direct, or indirect bilirubin, not accompanied by elevations of ALT or AST should be managed according to the discretion of the treating physician.

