- n. The patient has a history of prior exposure to a monoclonal antibody targeting the CGRP pathway (AMG 334, ALD304, LY2951742, or fremanezumab). If the patient has participated in a clinical study with any of these monoclonal antibodies, it has to be confirmed that the patient received placebo in order to be eligible for this study.
- o. The patient has any finding in the baseline 12-lead ECG considered clinically significant in the judgment of the investigator.
- p. The patient has any finding that, in the judgment of the investigator, is a clinically significant abnormality, including serum chemistry, hematology, coagulation, and urinalysis test values (abnormal tests may be repeated for confirmation).
- q. The patient has hepatic enzymes (alanine aminotransferase and aspartate aminotransferase)  $>1.5 \times$  the upper limit of normal (ULN) range after confirmation in a repeat test, or the patient has suspected hepatocellular damage that fulfills criteria for Hy's law at screening.
- r. The patient has serum creatinine  $>1.5 \times$  the ULN or evidence of clinically significant renal disease in the judgement of the investigator.
- s. The patient cannot participate or successfully complete the study, in the opinion of their healthcare provider or the investigator, for any of the following reasons:
  - mentally or legally incapacitated or unable to give consent for any reason
  - in custody due to an administrative or a legal decision, under tutelage, or being admitted to a sanitarium or social institution
  - unable to be contacted in case of emergency
  - has any other condition, which, in the opinion of the investigator, makes the patient inappropriate for inclusion in the study

- t. The patient is an employee of the sponsor/participating study center who is directly involved in the study or is the relative of such an employee.
- u. The patient has an active implant for neurostimulation used in the treatment of CH.
- v. The patient is a member of a vulnerable population (eg, people kept in detention).
- w. The patient has a history of alcohol and/or drug abuse that in the investigator’s opinion could interfere with the study evaluations or the patient’s safety.

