## 4. SELECTION AND WITHDRAWAL OF PATIENTS

Prospective waivers (exceptions) from study inclusion and exclusion criteria to allow patients to be enrolled are not granted by Teva (see [Appendix C](#)). Any deviation from the eligibility criteria will result in study drug discontinuation in the event that a patient has not been dosed.

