- n. The patient has a history of prior exposure to a monoclonal antibody targeting the CGRP pathway (AMG 334, ALD304, LY2951742, or fremanezumab). If the patient has participated in a clinical study with any of these monoclonal antibodies, it has to be confirmed that the patient received placebo in order to be eligible for this study.
- o. The patient has any finding in the baseline 12-lead ECG considered clinically significant in the judgment of the investigator.
- p. The patient has any finding that, in the judgment of the investigator, is a clinically significant abnormality, including serum chemistry, hematology, coagulation, and urinalysis test values (abnormal tests may be repeated for confirmation).
- q. The patient has hepatic enzymes (ALT and AST)  $>1.5 \times$  the upper limit of normal (ULN) range after confirmation in a repeat test, or the patient has suspected hepatocellular damage that fulfills criteria for Hy's law at screening.
- r. The patient has serum creatinine  $>1.5 \times$  the ULN or evidence of clinically significant renal disease in the judgement of the investigator.
- s. The patient cannot participate or successfully complete the study, in the opinion of their healthcare provider or the investigator, for any of the following reasons:
  - mentally or legally incapacitated or unable to give consent for any reason
  - in custody due to an administrative or a legal decision, under tutelage, or being admitted to a sanitarium or social institution
  - unable to be contacted in case of emergency
  - has any other condition, which, in the opinion of the investigator, makes the patient inappropriate for inclusion in the study

- t. The patient is an employee of the sponsor/participating study center who is directly involved in the study or is the relative of such an employee.
- u. The patient has an active implant for neurostimulation used in the treatment of CH.
- v. The patient is a member of a vulnerable population (eg, people kept in detention).
- w. The patient has a history of alcohol and/or drug abuse that in the investigator’s opinion could interfere with the study evaluations or the patient’s safety.

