##### **7.4.1. Serum Chemistry, Hematology, and Urinalysis**

Clinical laboratory tests (serum chemistry, hematology, and urinalysis) will be performed at the time points detailed in [Table 2](#). Clinical laboratory tests will be performed using the central laboratory. However, in case of abnormal coagulation during screening (run-in period) or if other specific urgent tests are required, a local retest can be authorized by the sponsor or designee on a case-by-case basis. Specific laboratory tests to be performed are provided in [Appendix M](#).

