### **2. Procedures Before Administration of Investigational Medicinal Product (Baseline [Visit 2, Day 0+3 day(s)])**

Patients who meet the inclusion and exclusion criteria at visit 1 will continue to visit 2 (week 0), when baseline assessments will be conducted.

The following procedures will be performed at visit 2 (week 0):

- Review inclusion/exclusion criteria.
- Review study compliance.
- Review electronic diary data including compliance.
- Perform triplicate 12-lead ECGs.
- Perform vital signs measurements (includes systolic and diastolic blood pressure, pulse, and body temperature).
- Perform a physical examination (including weight).
- Inquire about adverse events.
- Inquire about concomitant medications.
- Perform clinical laboratory tests (serum chemistry, hematology, coagulation, and urinalysis).
- Perform urine  $\beta$ -HCG pregnancy test (for women of childbearing potential only).
- Record CH attack information in the electronic diary device. Note: this will be completed by the patient at home, not during the investigational site visit.
- Obtain a 4-mL blood sample for pharmacokinetics analysis from either arm.
- Obtain a 5-mL blood sample for ADA analysis.
- Obtain a 6-mL blood sample for pharmacogenomics analysis.
- Obtain blood sample for biomarker analysis (8.5-mL serum, 6 mL plasma, and 2.5 mL for ribonucleic acid [RNA]).
- Obtain a 5-mL urine sample for biomarker analysis.
- Administer the HADS, EQ-5D questionnaire, SF-12, and WPAI questionnaire.
- Each patient's partner/family member completes the Impact on Partner and Family questionnaire. Partners/family members will be asked to attend the study visit with the patient. Partners/family members will be asked to attend the study visit with the patient or to return to the investigational center within  $\pm 3$  days of the patient's visit if unable to appear at the same time.
- Complete the PPSI.
- Complete the eC-SSRS Since Last Visit version.

Patients who meet eligibility criteria will be randomized to 1 of the treatment groups.

Eligible patients who consented to participate in the wearable sensor substudy, who are able to demonstrate appropriate use of the wearable device, and who are willing to comply with the requirements for use of the digital wearable device will be given the wearable device and accessories. The device will be worn on the wrist throughout the 12-week double-blind treatment period.

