4.2. Specification of Baseline Values

Baseline is the last observed data before the administration of the first dose of the IMP, unless otherwise noted. For data collected in the e-diary daily, baseline will be derived from the run-in period (including days from the informed consent up to the day prior to the first dose of the IMP administration) and prorated to 28 days if the number of days in the run-in period is not equal to 28. Details are provided in Section 6.1.

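### Appendix J treats baseline ALT or AST of 2–3 × ULN as enrollable, against exclusion q once the rise is confirmed, and its confirmation and stopping rules disagree from 3 × ULN; the effect is limited and wording can fix it

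*Protocol*

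**What the plan says.** **Entry.** Exclusion q in Protocol Section 4.2 begins "The patient has hepatic enzymes (ALT and AST"; the synopsis version begins "The patient has hepatic enzymes (alanine aminotransferase and aspartate aminotransferase". Both set the limit at more than 1.5 × ULN, conditional on a repeat test, and both add a separate limb for suspected Hy's law cases at screening. Section 4 states: "Prospective waivers (exceptions) from study inclusion and exclusion criteria to allow patients to be enrolled are not granted by Teva". The opening guidance of Appendix J asks for a liver-focused history and examination once ALT or AST reaches 2 × ULN. In parentheses it includes patients whose baseline is 2 to 3 × ULN, "who may be enrolled in the study". A later monitoring tier in the same appendix provides for baselines above 2.5 × ULN.

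**Timing of the baseline value.** Appendix B (visit 2, before dosing) says: "Patients who meet the inclusion and exclusion criteria at visit 1 will continue to visit 2 (week 0), when baseline assessments will be conducted". Blood is drawn and the first dose given at that same visit. Section 7.4.1 says: "Clinical laboratory tests will be performed using the central laboratory". SAP Section 4.2 says: "Baseline is the last observed data before the administration of the first dose of the IMP".

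**Stopping.** In Appendix J, the subsection on ALT or AST of at least 3 × ULN makes confirmation a precondition for stopping treatment and exempts only values of at least 8 × ULN. With a normal baseline, a value counts as confirmed if it is still at least 3 × ULN on repeat. With a baseline above ULN, it must be at least twice baseline. The Stopping Rules subsection orders immediate discontinuation at 3 × ULN or more with INR above 1.5 × ULN, with total bilirubin above 2 × ULN, or with liver symptoms not explained by another disease. It orders the same for 5 to below 8 × ULN persisting at least 2 weeks, and for 8 × ULN or more.

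**The concern.** Two sets of operative thresholds do not agree.

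At entry, the whole 2 to 3 × ULN range that Appendix J describes as enrollable lies above q's limit of 1.5 × ULN. A site that reads Appendix J as a permission could admit a patient whom q excludes.

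On treatment, a site faces one instruction to confirm before stopping and another to stop at once, and no text says which prevails. Because the confirmation subsection names its own single exemption, it can be read as deliberately leaving out the bilirubin, INR and symptom cases.

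Liver enzyme elevation is a listed potential risk (Section 1.3.1), and there is no Data Monitoring Committee (Section 5.9.3), so the rules applied at the site need to be clear. The reading also affects follow-up. The hepatitis and autoimmune serology is triggered by confirmation. The early withdrawal visit and at least 30 days of weekly enzymes are triggered by meeting a stopping rule. A site that waits for a confirmation that never comes could miss both.

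**Working it through.** This point rests on no sample-size or power figure, so there is none to reproduce. The check compares the texts and works through the thresholds.

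**Step 1: who can enter with a baseline of 2 to 3 × ULN?** I read baseline in Appendix J as the last pre-dose value, as SAP 4.2 defines it.

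- Rise in both enzymes, confirmed before randomisation: excluded by q, described as enrollable by Appendix J. This is the conflict.
- Eligible at screening, raised in the visit 2 pre-dose sample: not confirmed, so q's numeric limit does not apply. The sample goes to the central laboratory, and no text requires the result before dosing.
- Raised at screening and never repeated: q's limit applies only after a repeat, and no text obliges the site to do one.
- Confirmed rise in one enzyme only: escapes q if ALT and AST is read to mean that both must be raised. Other liver thresholds in the protocol use or (Sections 7.1.5.1 and 7.1.7, and Appendix J).

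So three kinds of patient could still enter with such a baseline. Appendix J names none of them and reads as a general permission.

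**Step 2: confirmation level when baseline is above ULN.** Formula: confirmation level = 2 × baseline. A gap exists where a value meets the level of a stopping rule but lies below the confirmation level. The baselines are illustrative.

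| Baseline (× ULN) | Confirmed at (× ULN) | Gap for rules starting at 3 × ULN (bilirubin, INR or symptoms) | Gap for the rule at 5 to <8 × ULN for ≥2 weeks |
|---|---|---|---|
| 1.5 | 2 × 1.5 = 3.0 | none | none |
| 2.0 | 2 × 2.0 = 4.0 | 3 to <4 | none |
| 2.5 | 2 × 2.5 = 5.0 | 3 to <5 | none |
| 3.0 | 2 × 3.0 = 6.0 | 3 to <6 | 5 to <6 |

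At q's limit of 1.5 × ULN the confirmation level equals the 3 × ULN trigger, so there is no gap. The gap opens only for baselines above q's limit.

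**Step 3: example.** Baseline 2.5 × ULN, then 4 × ULN with bilirubin above 2 × ULN. The value is at least 3 × ULN, so the first stopping rule is met, as are the ALT/AST and bilirubin levels of the Hy's law definition in Section 7.1.5.1. It is below 5 × ULN, so it is not confirmed.

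**Step 4: timing at any baseline.** Even with a normal baseline, values of 3 to below 8 × ULN need a repeat under one subsection, while the other says stop at once if bilirubin, INR or symptoms qualify.

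**The case against.** The strongest reply is that this is an editorial slip with little consequence.

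Sections 4.1 and 4.2 govern entry, Section 4 refuses waivers, and an ineligible patient who has not been dosed must not be dosed. The disputed words are a parenthesis in a monitoring appendix headed as guidance, and some patients can properly have such a baseline, so the words may merely describe them. ALT and AST is most naturally a list of the enzymes meant. Exclusion e remains, as does exclusion p, which turns on the investigator judging a finding to be a "clinically significant abnormality, including serum chemistry, hematology, coagulation, and urinalysis test values".

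On stopping, site staff give the drug only at weeks 0, 4 and 8, and the half-life is about 32 to 36 days. Stopping at once and stopping after a repeat therefore differ only if a dose falls due in between, and the repeat may be done locally. The Stopping Rules carry no confirmation condition. Section 7.1.7 makes ALT or AST of 3 × ULN or more, or bilirubin of 2 × ULN or more, an event of special interest, reported like a serious adverse event. Section 4.3 requires withdrawal when the investigator judges that an adverse event makes continuing contrary to the patient's interest.

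Most of this stands, and it limits the harm. It does not remove the contradictions: the parenthesis is not confined to unconfirmed rises, and the confirmation sentence exempts only 8 × ULN.

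A reader might infer that the protocol admits confirmed 2 to 3 × ULN patients as a class, or that a patient with a Hy's law pattern would go on being dosed. The documents support neither. Admitting the first patient would breach q and Section 4; the second already meets a rule ordering immediate discontinuation and is covered by the reporting and withdrawal provisions above.

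**Conclusion.** The concern holds as two inconsistencies in the text. Appendix J conflicts with exclusion q and the no-waiver rule for any patient whose rise is confirmed before randomisation. Its confirmation requirement also conflicts with its Stopping Rules from 3 × ULN when bilirubin, INR or symptoms qualify.

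The practical effect is limited. It arises mainly when a week 4 or week 8 dose falls due before the repeat result, or when a patient with a raised baseline never reaches twice baseline. The gap spans 1, 2 or 3 multiples of ULN for baselines of 2, 2.5 or 3 × ULN.

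This rests on baseline in Appendix J meaning the last pre-dose value. The one-enzyme route also depends on a literal reading of ALT and AST. The documents do not show how many patients would be affected. Sample size, power and the efficacy analysis do not change. The wording should still be corrected, because these are entry and stopping thresholds for a listed potential risk.

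**What to change.** 1. In the opening guidance of Appendix J, delete the words that permit enrolment. Keep the monitoring instruction, and the tier for baselines above 2.5 × ULN, for patients found to have a raised pre-dose baseline.
2. In exclusion q, in both the synopsis and Section 4.2, write ALT or AST, and require that a screening value above 1.5 × ULN be repeated before randomisation.
3. Amend the confirmation sentence itself so that it exempts every case meeting a stopping rule, not only 8 × ULN or more. State that the Stopping Rules apply at their stated ULN multiples regardless of the twice-baseline test. The rule for 5 to below 8 × ULN keeps its own requirement of at least 2 weeks' persistence. Adding a sentence elsewhere while leaving the confirmation sentence unchanged would preserve the contradiction.

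The cost is wording in two copies of q and in Appendix J, plus a repeat blood test for any patient with a raised screening value who would not otherwise have had one. No scheduled visit, sample size or analysis changes. The downside is an occasional discontinuation on a single unrepeated value, which the Stopping Rules already order.
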